8.1 Clinical assessments

Standard of Care Clinic Visits

Participants will be evaluated in the clinic prior to the start of therapy and study intervention, as well as at monthly intervals for history, physical examination for vitals, height, and weight. Hearth Hope Index (HHI), SF-36, cancer specific FACT-surveys, Brief Pain Inventory, and Brief Fatigue Inventory, and self-report diaries (adverse events, adherence and palatability surveys) will be completed to evaluate QOL and will be administered at baseline, monthly during the intervention and at study terminus. Serum or plasma-based biological markers will also be collected at baseline, and midpoint and study terminus. Standard of care brain imaging will be utilized at baseline, 8 and 16 weeks to evaluate disease status and progression. Body composition and bone mineral density will be assessed at baseline and 16 weeks using dual energy x-ray absorptiometry (DXA).

8.2 Adherence

Participant adherence with the study intervention will be encouraged and monitored in several ways. All participants will be provided a handheld glucometer (Precision Xtra, Abbott Nutrition) and reagent strips that measure BOHB from a small amount of blood obtained by finger stick. Although there is variability between people, BOHB levels in individuals consuming more than 100 grams of carbohydrate per day are usually ≤ 0.1 mmol/L. A primary goal of the initial diet intervention is for each participant to enter nutritional ketosis, which starts at 0.5 mM and extends up to approximately 3.5 mmol/L. This is a strong indication that fat is being used as one's primary fuel, and there may be other therapeutic benefits associated with ketones in this range. Transient increases in ketones above 3.5 mmol/L may occur after exercise, but regulatory feedback systems keep ketones from elevating to dangerous levels that are seen in uncontrolled type-1 diabetics who have insufficient insulin (i.e., >10 mmol/L). Participant's information will be kept private and only made available to IRB approved research staff. During the intervals between research- based visits participants will report their ketone levels daily to the research coordinator and lead RD on the team and adjustments to the diet made accordingly.

We will counsel patients to aim for a level > 1.0 mM while following principles of a well-formulated ketogenic diet. If ketone readings are lower than 0.5 mM, we will individually work with the patient to identify appropriate changes to their diet/lifestyle to achieve nutritional ketosis. The monitoring of daily ketones for patients on the ketogenic diet provides a gold-standard biofeedback marker that is objective and quantifiable for adherence. Deviation from the dietary standards of a well-formulated ketogenic diet will cause rapid decreases in ketones and elevations in blood glucose,

which will be identified in the patient:researcher interaction. For the standard diet arm, this will present a greater challenge. We will ask participants to inform us of dietary deviations and these will be identified and logged. The monthly self-report diaries will be used for tracking any minor adverse effects (GI distress, bloating, gut distension, diarrhea etc.). If participants do not experience any side effects, it is possible they will not have a self-report diary to share monthly.

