8.4 Safety Monitoring

Adverse events will be monitored by self-reporting of signs and symptoms. Patients will maintain weekly contact with researchers and any possible ill effects will be noted and discussed with the attending physician or Research Nurse to discuss and manage any possible side effects. Patients will be counseled with regard to potential signs of treatment toxicity and should immediately contact the PI, study coordinator or treating physician in the event such a problem arises.

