Psychological effects of the combinatory therapy will be evaluated using several inventories. The Hearth Hope Index is a 12-item adapted version of the Hearth Hope Scale designed to assess feelings of 'hope' within the patient. The Short Form-36 is a 36-item patient reported survey of patient health status. Each scale is transformed into a 0-100 score and includes eight sections: vitality, physical functioning, bodily pain, health perceptions, role functioning, emotional functioning, social functioning and mental health. Brief Pain Inventory is a short form used for clinical trials that rapidly evaluates the severity of pain and impact on body functioning, and the Brief Fatigue Inventory is used to evaluate the severity and impact cancer-related fatigue. To more directly assess the emotional and behavioral response to the diet initiation and maintenance we will employ the Functional Assessment of Anorexia/cachexia Treatment. The FAACT measures the general aspects of quality of life as well as specific anorexia and cachexia related concerns. These surveys will help to determine the individual's psychosocial response to the eating changes. Additionally, participants will be asked to maintain an event diary to determine diet palatability and any adverse event reporting. Inclusion of these surveys and diaries will provide important data on the feasibility of a ketogenic diet in patients with brain mets. Expected time for completion of the surveys is approximately 30 minutes.

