12.0 ADVERSE EVENT REPORTING

12.1 Definition

Adverse event: Any unfavorable and unintended sign (including abnormal laboratory finding), symptom, or disease temporally associated with the use of a medical treatment or procedure, regardless of whether it is considered related to the medical treatment or procedure; also an "unanticipated problem" of any nature (e.g., psychological or social harm) (designated as unrelated, definitely related, probably related, or possibly related; see below)

Serious adverse event: Any adverse event that is fatal or life threatening, is permanently disabling, requires inpatient hospitalization or prolongs hospitalization, or results in a congenital anomaly or birth defect

Life-threatening event: Any adverse event in which the subject is at immediate risk of death from the reaction as it occurs; does not include a reaction that, if it were to occur in a more serious form, might cause death

Unexpected event: Any adverse event that is not identified in nature, severity, or frequency in the investigator brochure, study protocol, consent form, or IND application; or the event was more serious than anticipated

Association:

Definitely Related: An adverse event that has a timely relationship to the administration of the investigational drug/study procedure and follows a known pattern of response which no alternative cause is present

Probably Related: An adverse event that has a timely relationship to the administration the investigational drug/study procedure and follows a known pattern of response, but which a potential alternative cause may be present

Possibly Related: An adverse event that has a timely relationship to the administration the investigational drug/study procedure, follows no known pattern of response, potential alternative cause does not exist

Unrelated: An adverse event for which there is evidence that it is definitely a related cause other than the investigational drug/agent; in general, no timely relationship administration of the drug/procedure exists, or if so, the event does not follow a pattern response and an alternative cause is present

The Common Terminology Criteria for Adverse Events v4.0 (CTCAE) of the National Cancer Institute will be used. The severity of adverse reactions is categorized as grade 1 to grade 5 in increasing severity. Grade 3, 4 and 5 toxicities will be reported as adverse events. General descriptors for the toxicity grades range from mild to fatal:

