12.2 Documentation

All adverse events must be documented in detail within the medical record. The patient will be observed and monitored carefully until the condition resolves, stabilizes, or its cause is identified. All adverse events, including laboratory abnormalities, will be followed up according to good medical practices. Information to be recorded includes the following:

a. Specific type of reaction.

b. Duration of reaction.

c. Severity/grade of reaction according to the NCI Common Terminology Criteria for Adverse Events v4.0 (CTCAE).

d. Suspected cause of the reaction (i.e. possibly or probably related to one of the following: study treatment, progression of disease, concurrent medications, concurrent illness, or other factors).

e. Changes made in the administration of the study drugs and other actions taken to alleviate the clinical event.

f. Patient's response to medical interventions.

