17.0 STATISTICAL ANALYSES

Analysis Plan

Unless otherwise specified, all analyses will proceed on an intent-to-treat basis, and hypothesis tests will be two-sided and at the 5% significance level.

The primary objective is to assess the feasibility of maintaining a ketogenic versus AICR diet in patients with brain metastasis selected for radiosurgery. The primary measurements are blood levels of glucose and ketones. Measurements will be taken at baseline, 8 weeks, and 16 weeks. These biomarker outcomes will be analyzed using mixed effects linear regression with fixed effects for timepoint, diet group, their interaction, BMI, and sex. We will use subject-level intercept random effects to account for correlation between repeated measurements within subjects. The primary targets of inference are the treatment effects at each (post-baseline) timepoint. To test the two primary measurements at the two post-baseline timepoints, we will use a 4-way Bonferroni-Holm correction to account for multiplicity. Retention at week 8 and 16, as well as side effects, will be summarized and compared between diet groups.

To assess the preliminary efficacy of ketogenic versus AICR diet on tumor response to targeted radiation therapy, we will use a Chi-squared test for the association between treatment group and partial-or-complete response according to RECIST v1.1.

For the exploratory objective assessing the preliminary effects of the ketogenic versus AICR diet on quality of life in BM individuals undergoing radiation therapy, we will use the same linear mixed effects model as for the primary objective, but with the following quality-of-life endpoints as outcomes: Hearth Hope Index, SF-36, FACT-B, Brief Pain Inventory, and Brief Fatigue Inventory. Tests will be performed without multiplicity correction.

The mixed models used for the primary analyses are applicable to unbalanced data due to chance imbalances, missing data, or drop-out. We will assess the possible impact of non-random missingness using sensitivity analyses.

Power Analysis

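### Event-free participants may return no monthly diary, so 'no side effects' cannot be told from 'diary not returned' in an outcome that is compared between arms

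*Protocol*

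**What the plan says.** Protocol section 5.0 lists side-effects under the primary feasibility objective; only glucose and ketones are marked there as primary endpoints. Section 17.0 says: "Retention at week 8 and 16, as well as side effects, will be summarized and compared between diet groups". It does not name the data source or the grades.

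For the mild events expected from a diet change, section 8.2 names the instrument: "The monthly self-report diaries will be used for tracking any minor adverse effects (GI distress, bloating, gut distension, diarrhea etc". It goes on: "If participants do not experience any side effects, it is possible they will not have a self-report diary to share monthly".

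Two other places treat the diary as something everyone keeps. Section 8.1 says: "self-report diaries (adverse events, adherence and palatability surveys) will be completed to evaluate QOL and will be administered at baseline, monthly during the intervention", and again at the end of the study. Section 9.0 says: "participants will be asked to maintain an event diary to determine diet palatability and any adverse event reporting".

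There are further sources of side-effect data. Section 8.4 says: "Patients will maintain weekly contact with researchers and any possible ill effects will be noted". Section 11 has toxicity monitored with CTCAE at study visits and telephone calls. The adherence and retention text under the dietary interventions puts all enrolled participants in daily correspondence with staff.

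On grades, section 12.1 (and the same sentence in section 11) says: "Grade 3, 4 and 5 toxicities will be reported as adverse events". Section 12.2 says: "All adverse events must be documented in detail within the medical record", and asks for the grade of each.

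**The concern.** The diary is the only tool the protocol names specifically for minor events such as bloating and diarrhoea. If a participant with nothing to report need not hand one in, a blank month from that person looks the same as a blank from someone who forgot, felt too ill or was leaving the study. The diary also carries adherence and palatability, so a participant who uses the exemption loses those feasibility data too.

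This is a fault of collection. An analysis plan can say how blanks are counted, but it cannot recover what a blank meant if an explicit 'none' was never asked for. What is at stake is the tolerability comparison in a pilot whose stated purpose is feasibility.

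**Working it through.** **The plan's own figure.** The only design figure is 99% power for glucose and ketones (section 17.0, Power Analysis), with 12 completers per arm and alpha 0.0125. Using the noncentral t with 22 degrees of freedom and noncentrality (difference/SD) × √6:
- Glucose: 2.3/1.077 × √6 = 5.23, power 99.05%.
- Ketones: 0.34/0.16 × √6 = 5.21, power 98.99%.

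The figure reproduces, and nothing below changes it. The protocol has no figure for side effects.

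**The texts side by side.** Sections 8.1 and 9.0 expect a diary from participants generally, and section 8.1 expects it monthly. Section 8.2 accepts none from someone who was well. Under sections 8.1 and 9.0 a blank is missing data. Under section 8.2 it may be a valid nil report. No text separates the two.

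**How much it could matter.** Let p be the true share of an arm with a minor side effect, r the chance that the diary is returned when there was an event, and w the chance that contacts or visits catch an event the diary missed. If blanks were counted as event-free:

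observed rate = p × [1 − (1 − r)(1 − w)]

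All of p, r and w are assumptions; the protocol gives none of them.

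*Same true rate (p = 50%), return after an event 90% in one arm and 60% in the other:*

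| w | Arm with 90% return | Arm with 60% return | False difference |
|---|---|---|---|
| 0 | 0.5 × 0.90 = 45% | 0.5 × 0.60 = 30% | 15 points |
| 0.5 | 0.5 × 0.95 = 47.5% | 0.5 × 0.80 = 40% | 7.5 points |
| 0.9 | 0.5 × 0.99 = 49.5% | 0.5 × 0.96 = 48% | 1.5 points |
| 1 | 50% | 50% | 0 |

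At w = 0 the false difference is p × 0.30, so it runs from 9 points (p = 30%) to 21 points (p = 70%). With equal 80% return and w = 0, both arms show 40%: each rate is too low, but the difference is still zero.

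*Different true rates (60% and 30%, a true difference of 30 points), w = 0:*
- Return 80% in both arms: 48% − 24% = 24 points.
- Return 90% and 60%: 54% − 18% = 36 points.
- Return 60% and 90%: 36% − 27% = 9 points.

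Under this counting the rates can only fall. The difference can shrink, grow or stay the same.

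**What an explicit 'none' entry buys.** Blanks could then be counted as missing. With m of 12 participants in an arm missing and no other source, the arm's rate is known to within m/12: 8 points for m = 1, 17 for 2, 25 for 3 and 33 for 4.

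**The case against.** The strongest reply is that the diary does not stand alone. Staff are in weekly contact with patients and note ill effects, toxicity is graded at visits and calls, correspondence is daily in both arms, and every adverse event must be documented. This stands, and it is why the effect may be small: if these channels catch 90% of what the diaries miss, the 15-point example falls to 1.5. It does not close the point. Section 8.4 relies on self-reported signs and symptoms and sets no common list of questions, the share that would be caught is unknown, and section 17.0 does not say that these channels feed the comparison.

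Four stronger readings are tempting, and the documents do not support them:
- A reader might infer that a missing diary is scored as no side effects. No coding rule says so. Section 8.2 only allows that the diary may be absent, and the counting rule may sit in an analysis plan that is not shown.
- A reader might infer that only Grade 3 to 5 events enter the comparison. Sections 11 and 12.1 limit what is reported as an adverse event, section 12.2 requires all events to be documented, and section 17.0 sets no grade limit. The texts fit badly together, but that is not an exclusion.
- A reader might infer that closer contact in the ketogenic arm tilts the result. The daily correspondence covers both arms, and the greater challenge that section 8.2 mentions for the standard diet concerns dietary deviations.
- A reader might infer that a diet people abandon would pass as well tolerated. Retention is compared by arm at weeks 8 and 16, and section 15 requires reasons for discontinuation to be documented.

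**Conclusion.** The point holds as a conflict in data collection. Section 8.2 disagrees with section 8.1 and leaves a blank diary without a meaning. Minor side-effect rates may be understated, and the between-arm comparison may be biased in an unknown direction.

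The size cannot be fixed from the protocol. Under the assumed 50% rate and 90% against 60% return, it lies between 0 and 15 points depending on what other contacts catch; 15 points is 1.8 patients in an arm of 12. All of these figures rest on blanks being counted as event-free, which the protocol does not state. A bias in favour of either diet is not shown.

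The primary glucose and ketone tests, their power and the sample size of 24 are untouched. This is a worthwhile and nearly free improvement that does not threaten the main analysis.

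**What to change.** - Replace the section 8.2 sentence with a required monthly return from every participant in both arms, including an explicit 'none' entry. Prompt it at contacts that already take place, with the same side-effect questions in both arms.
- Treat an absent diary as missing rather than event-free. Report diary return by arm next to retention, because a rate based on returned diaries alone leaves out people who were too ill or had left.
- State in section 17.0 that the side-effect comparison uses all grades, drawn from diaries and contacts together.
- Reconcile sections 8.1, 8.2, 11, 12.1 and 12.2 on who completes the diary and on which events are recorded and which are reported. Expedited reporting can stay as it is.

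The cost is a tick box, a reminder and slightly more data entry. The 'none' entry has to be collected during the trial, since it cannot be reconstructed afterwards.

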8.3 Data and Records

Primary source documents will include forms routinely used at the James Comprehensive Breast Center, namely the Breast Patient Information Form, clinic and office notes as well as laboratory and radiology reports.

8.4 Safety Monitoring

Adverse events will be monitored by self-reporting of signs and symptoms. Patients will maintain weekly contact with researchers and any possible ill effects will be noted and discussed with the attending physician or Research Nurse to discuss and manage any possible side effects. Patients will be counseled with regard to potential signs of treatment toxicity and should immediately contact the PI, study coordinator or treating physician in the event such a problem arises.

8.5 Accountability

All interventional testing will be provided at no cost to the patient. Further, as a result of the timeintensive nature of the study participants in the intervention group will receive a completion stipend of \$500.

9.0 BIOCHEMICAL, COGNITIVE AND PSYCHOSOCIAL TESTING

Activity Monitor:

Physical activity during a course of radiation therapy can be associated with decreased fatigue and may potentially mitigate other side effects. An activity tracker will be worn around the wrist daily for heart rate and step counting.

Peripheral Blood Samples:

Additional lab samples, which are not part of standard care, will be obtained at baseline and paid for as a research cost. Blood will be collected at baseline and every 8 weeks throughout the study duration until terminus.

Continuous Glucose Monitoring (CGM)/ Continuous Ketone Monitoring (CKM):

In order to more accurately quantify the glycemic control and diet adherence of patients using either the AICR or Ketogenic diet we will use three 10-14 day recording periods of CGM/CKM at baseline, midpoint and post-testing. A small Bluetooth compatible unit will be affixed to either the triceps or adipose located near anterior superior iliac spine. CGM/CKM will be analyzed for glucose excursions, mean glucose levels and other markers of glycemic control.

Insulin Resistance and Pre-Diabetes Panels

Due to the high correlation between insulin resistance, diabetes and breast cancer occurrence/prognosis, we will examine the effects of the two diets on several biomarkers including HbA1c, Insulin, Glucose, and Sex hormone binding globulin (SHBG).

Inflammation Panel

Due to the fact that anti-cancer therapies result in increased inflammation, we will examine a panel

of inflammation markers. Each of the following markers is associated with either prognosis or quality of life. The markers to be assessed will be: $TNF-\alpha$ IL-6, IL- 8, CD-14, and CD-16.

Collection and Handling of Specimens

At baseline, and on a monthly basis until study terminus blood will be collected from the participant. Prior to testing all vacutainers will be labeled per study requirements. Blood will be collected into vacutainers, inverted and then stored depending on requirements for each assay.

Cognitive Testing

The current trial will build on the successes of RTOG 0614 and NRG-CC001 in utilizing the same neurocognitive function (NCF) measures with the addition of the PROMIS Cognitive Function Short Form 8a self-report assessment. There are a number of advantages of such an approach including familiarity and acceptance of these measures by clinical research staff, the well-established use and validation of these measures in brain metastasis research, and the possibility of future post-hoc analyses between studies.

The NCF tests to be used in this study (the Hopkins Verbal Learning Test – Revised (Benedict 1998), Trail Making Test (Tombaugh 2004), and the Controlled Oral Word Association (Ruff 1996) are the same tests as were used in RTOG 0614, NRG-CC001, NCCTG/Alliance N0574, and NCCTG/Alliance N107C, and that are being used in numerous ongoing brain met trials (e.g., NRG-CC003, SWOG S1827).

While NCF outcomes have been recognized as being crucial in the brain metastasis population (Lin 2013), there is also interest in evaluating the impact of treatment arm on patient-reported outcomes. PROMIS Cognitive Function Short Form 8a measures perceived cognitive abilities (e.g., memory, attention, and decision making) and the application of such abilities to everyday tasks (e.g., planning, organizing, calculating, remembering and learning). The PROMIS-8, assessment is brief and therefore not a significant burden for patients to complete.

The Hopkins Verbal Learning Test – Revised (Benedict 1998), Trail Making Test (Tombaugh 2004), and the Controlled Oral Word Association test (Ruff 1996) are widely used and standardized psychometric instruments that have been shown to be sensitive to the impact of cancer and the neurotoxic effects of cancer treatment in other clinical trials (Gilbert 2014; Meyers 2004; Wefel 2011). The tests have published normative data that account for age and, where appropriate, education and gender. The NCF assessments will be administered at baseline, 8 and 16 weeks.

The established metric for clinically-significant change is the Reliable Change Index (RCI; Jacobsen 1991). The RCI is derived from the standard error of measurement of each test and represents the 90% confidence interval for the difference in raw score from baseline to the next assessment that would be expected if no real change occurred:

RCI = 1.64(standard error of difference), where standard error of difference

= $[2(\text{standard error of measure}^2)]^{1/2}$, and standard error of measure

= standard deviation₁[$(1 - r_{xy})^{1/2}$]

This yields the following RCI values for each test in the Clinical Trial Battery:

NCF Test	RCI Value
HVLT-R Total Recall	5
HVLT-R Delayed Recall	3

HVLT-R Delayed Recognition	2
TMT Part A	12
TMT Part B	26
COWA	12

At each assessment, change in raw test score relative to baseline are calculated, and declines in a score that meets or exceeds the RCI value is categorized as a failure. **Cognitive failure (CF)** is defined as a decline on at least one of the Clinical Trial Battery tests (HVLT-R, TMT, COWA) that meets or exceeds the RCI value.

PROMIS Cognitive Function Short Form 8a v2.0: This measure is a 8-item questionnaire that assesses patient-perceived cognitive concerns over the past 7 days. The 8-item short form has demonstrated excellent internal consistency reliability and has criterion validity related evidence for measuring cognitive concerns but not cognitive performance. This measure asks the patient to rate the frequency of the following cognitive complaints over the preceding 7 days. Each question has five response options ranging in value from one to five (with lower scores indicating more severe cognitive concerns). The total raw score for a short form would be the sum of the values of the response to each question (therefore, for a short form which all questions are answered, the lowest possible score is 8 and the highest possible raw score is 40).

Collection of Psychosocial and Behavioral Inventories

Psychological effects of the combinatory therapy will be evaluated using several inventories. The Hearth Hope Index is a 12-item adapted version of the Hearth Hope Scale designed to assess feelings of 'hope' within the patient. The Short Form-36 is a 36-item patient reported survey of patient health status. Each scale is transformed into a 0-100 score and includes eight sections: vitality, physical functioning, bodily pain, health perceptions, role functioning, emotional functioning, social functioning and mental health. Brief Pain Inventory is a short form used for clinical trials that rapidly evaluates the severity of pain and impact on body functioning, and the Brief Fatigue Inventory is used to evaluate the severity and impact cancer-related fatigue. To more directly assess the emotional and behavioral response to the diet initiation and maintenance we will employ the Functional Assessment of Anorexia/cachexia Treatment. The FAACT measures the general aspects of quality of life as well as specific anorexia and cachexia related concerns. These surveys will help to determine the individual's psychosocial response to the eating changes. Additionally, participants will be asked to maintain an event diary to determine diet palatability and any adverse event reporting. Inclusion of these surveys and diaries will provide important data on the feasibility of a ketogenic diet in patients with brain mets. Expected time for completion of the surveys is approximately 30 minutes.

